13.1.3 Toxicity

13.1.3.1 Serious Adverse Events

A review of the AstraZeneca Patient Safety database (which includes AstraZeneca-sponsored, investigator-sponsored/collaborative group monotherapy studies and Managed Access Program reports) as of 15 June 2016 identified a total of 1413 SAEs (1093 unblinded, 320 blinded) received from 752 patients in olaparib monotherapy studies. SAE reports of $\geq 1\%$ (≥ 36 patients treated with olaparib/placebo monotherapy) were anemia (n=143), abdominal pain (n=40), vomiting (n=47), nausea (n=42) and dyspnea (n=41). The most commonly reported SAEs from these monotherapy studies were similar for the tablet and capsule formulation.

13.1.3.2 Frequent Adverse Events

- Most common adverse reactions and laboratory abnormalities in clinical trials were anemia, nausea, fatigue (including asthenia), vomiting, diarrhea, dysgeusia, dyspepsia, headache, decreased appetite, nasopharyngitis/pharyngitis/URI, cough, arthralgia/musculoskeletal pain, myalgia, back pain, dermatitis/rash, abdominal pain/discomfort, increase in creatinine, mean corpuscular volume elevation, decrease in hemoglobin, decrease in lymphocytes, decrease in absolute neutrophil count, and decrease in platelets.
- The following adverse reactions and laboratory abnormalities have been identified in ≥10 to <20% of the 223 patients receiving olaparib: cough, constipation, dysgeusia, peripheral edema, back pain, dizziness, headache, urinary tract infection, dyspnea, and rash.
- The following adverse reactions and laboratory abnormalities have been identified in ≥1 to <10% of the 223 patients receiving olaparib and not included in the table: leukopenia, stomatitis, peripheral neuropathy, pyrexia, hypomagnesemia, hyperglycemia, anxiety, depression, insomnia, dysuria, urinary incontinence, vulvovaginal disorder, dry skin/ eczema, pruritus, hypertension, venous thrombosis (including pulmonary embolism), and hot flush.

13.1.3.3 Warnings and Precautions

- Myelodysplastic syndrome/Acute Myeloid Leukemia: (MDS/AML) occurred in patients exposed to olaparib, and some cases were fatal. Monitor patients for hematological toxicity at baseline and monthly thereafter. Discontinue if MDS/AML is confirmed.
- Pneumonitis: occurred in patients exposed to olaparib, and some cases were fatal. Interrupt treatment if pneumonitis is suspected. Discontinue if pneumonitis is confirmed.

• Embryo-Fetal toxicity: olaparib can cause fetal harm. Advise females of reproductive potential of the potential risk to a fetus and to avoid pregnancy.

13.1.4 Formulation and preparation

Olaparib tablets are supplied as green, film-coated tablets in 100 mg and 150 mg strengths. The 100 mg strength is also available as a yellow, film-coated tablet.

- 100 mg tablets are 14.5 mm x 7.25 mm oval-shaped
- 150 mg are 14.5 mm x 7.25 mm oval-shaped

Olaparib tablets will be packed in high-density polyethylene (HDPE) bottles with child-resistant closures. Each dosing container will contain 32 tablets. Olaparib sufficient for 1 21-day cycle + 3 additional days in case of vomiting will be dispensed to patients on Day 1 at the beginning of each subsequent cycle until the patient completes the study, withdraws from the study or closure of the study.

Tablet core components include active drug substance, copovidone, colloidal silicon dioxide, mannitol and sodium stearyl fumarate. Film coating contains hydroxypropyl methylcellulose (hypromellose), macrogol 400 (polyethylene glycol 400), titanium dioxide, iron oxide yellow and iron oxide black. The yellow tablet film coating only differs from the green film coating with the omission of iron oxide black.

13.1.5 Stability and Storage

All study drugs should be kept in a secure place under appropriate storage conditions. Store in a secure location below 30° C (86° F). Sites are not permitted to re-package tablets. Once the bottle is opened, olaparib tablets must be used within 3 months of the opening date; unused tablets should be discarded. Instruct patients not to open a bottle until they are ready to use it.

13.1.6 Administration Procedures

Please refer to section 3.2.

13.1.7 Incompatibilities

CYP3A Inhibitors: Avoid concomitant use of strong and moderate CYP3A inhibitors. If the inhibitor cannot be avoided, the dose may be reduced as allowed by protocol.

CYP3A Inducers: Avoid concomitant use of strong and moderate CYP3A inducers. If a moderate CYP3A inducer cannot be avoided, be aware of a potential for decreased efficacy.

13.2 CLINOMICS PLATFORM (NSR DEVICE)

13.2.1 Source

The platform was developed in house by the Center for Cancer Research and is available for use by investigators at the NCI. Testing will be performed in the NCI Laboratory of Pathology (CLIA#21D0716664) and/or ClinOmics (CLIA# 21D2125203)

13.2.2 Toxicity

None. However, participants may experience non-physical risks of genetic research as described in section 12.4.3.

15 APPENDICES

15.1 APPENDIX A – PERFORMANCE STATUS CRITERIA

| ECOG Pe | erformance Status Scale | Karnofsky Performance Scale | | |
|---------|--|-----------------------------|--|--|
| Grade | Descriptions | Percent | Description | |
| | Normal activity Fully active able | 100 | Normal, no complaints, no evidence of disease. | |
| 0 | to carry on all pre-disease performance without restriction. | 90 | Able to carry on normal activity; minor signs or symptoms of disease. | |
| | Symptoms, but ambulatory. Restricted in physically strenuous | 80 | Normal activity with effort; some signs or symptoms of disease. | |
| 1 | to carry out work of a light or sedentary nature (e.g., light housework, office work). | 70 | Cares for self, unable to carry on normal activity or to do active work. | |
| 2 | In bed <50% of the time. Ambulatory and capable of all self-care, but unable to carry out any work activities. Up and about more than 50% of waking hours. | 60 | Requires occasional assistance, but is able to care for most of his/her needs. | |
| | | 50 | Requires considerable assistance and frequent medical care. | |
| 2 | In bed >50% of the time. Capable of only limited self-care, confined to bed or chair more than 50% of waking hours. | 40 | Disabled, requires special care and assistance. | |
| 5 | | 30 | Severely disabled, hospitalization indicated. Death not imminent. | |
| 4 | 100% bedridden. Completely disabled. Cannot carry on any self- care. Totally confined to bed or chair. | 20 | Very sick, hospitalization indicated. Death not imminent. | |
| | | 10 | Moribund, fatal processes progressing rapidly. | |
| 5 | Dead. | 0 | Dead. | |

15.2 APPENDIX B -COCKCROFT-GAULT FORMULA

Creatine Clearance (mL/min) = (140 - age) x weight in kg (x 0.85 for females) (serum creatinine [mg/dL] x 72)

15.3 APPENDIX C - PARTICIPANT OLAPARIB PILL DIARY

Today's date

Patient Name Patient Study ID

Cycle #

INSTRUCTIONS TO THE PATIENT:

- 1. Complete one form for each cycle (21 days).
- 2. You will take olaparib tablets twice a day ~12 hours apart on every day of the cycle. You must take the tablets with a large glass of water. A light snack (biscuits/ toast) is also recommended to help reduce nausea.
- 3. The olaparib tablets should be swallowed whole and not chewed, crushed, dissolved or divided.
- 4. You should avoid drinking grapefruit juice while on study.
- 5. If you miss a scheduled dose, you may take the scheduled dose up to 2 hours after the scheduled dose time. If it is more than 2 hours after the scheduled dose time, do not take the missed dose. You should then take the next dose at the scheduled time.
- 6. If you miss more than half of the doses (21 tablets) in any cycle, we will have to remove you from the study.
- 7. Record the date, the number of tablets you took, and when you took them.
- 8. If you have any comments or notice any side effects, please record them in the Comments column.
- 9. Please bring your pill bottle and this form to your physician when you go for your next appointment.

| DAY | DATE | # Tablets and When Taken | COMMENTS (side effects or missed doses) |
|-----|------|--------------------------|---|
| 1 | | AM PM | |
| 2 | | AM PM | |
| 3 | | AM PM | |
| 4 | | AM PM | |
| 5 | | AM PM | |
| 6 | | AM PM | |

| DAY | DATE | # Tablets and When Taken | COMMENTS (side effects or missed doses) |
|-----|------|--------------------------|---|
| 7 | | AM PM | |
| 8 | | AM PM | |
| 9 | | AM PM | |
| 10 | | AM PM | |
| 11 | | AM PM | |
| 12 | | AM PM | |
| 13 | | AM PM | |
| 14 | | AM PM | |
| 15 | | AM PM | |
| 16 | | AM PM | |
| 17 | | AM PM | |
| 18 | | AM PM | |
| 19 | | AM PM | |

| DAY | DATE | # Tablets and When Taken | COMMENTS (side effects or missed doses) |
|-----|------|--------------------------|---|
| 20 | | AM PM | |
| 21 | | AM PM | |

| Patient's Signature: | D | Date: | |
|----------------------|---|-------|--|
|----------------------|---|-------|--|

The Study Team will complete this section:

- 1. Date patient started protocol treatment
- _____ 2. Date patient was removed from study therapy _____
- 3. Total number of pills taken this cycle (Days 1-21)

Physician/Nurse Signature _____

15.4 APPENDIX D – ACTIONS REQUIRED IN CASES OF LIVER BIOCHEMISTRY AND EVALUATION OF HY'S LAW

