3.2 DRUG ADMINISTRATION

Olaparib at the dose of 300 mg will be given orally continuously twice daily, with doses taken at the same times each day approximately 12 hours apart. The correct number of 100mg or 150mg tablets comprising the appropriate dose should be taken at the same times each day with approximately 240 mL of water. Doses may be taken with a light meal/snack. The olaparib tablets should be swallowed whole and not chewed, crushed, dissolved, or divided.

Olaparib will be dispensed at the start of each 21-day cycle. Per the CCR policy for selfadministered oral investigational agents (PM-8) which will be followed in this protocol, patients will be provided with a pill diary (Appendix C), instructed in its use, and asked to bring it with them to each appointment.

Patients should be given clear instructions on how and when to take their study treatment. Patients will self-administer olaparib. Study site staff will make tablet counts at regular intervals during treatment. Compliance will be assessed by the tablet count and the information will be recorded in the appropriate section of the eCRF. All patients must return their bottle(s) of olaparib at the appropriate scheduled visit, when a new bottle will be dispensed. Patients will be instructed to notify study site personnel of missed doses. Dates of missed or held doses will be recorded by the patient on their patient diary and by the site staff on the eCRF.

If a patient misses more than 50% of the doses in any given cycle, the patient will be considered inevaluable for response per sections 10.3.2 and 10.3.3 and will be removed from the study.

Patients must return all containers and any remaining tablets at the end of the study.

If vomiting occurs shortly after the olaparib tablets are swallowed, the dose should only be replaced if all of the intact tablets can be seen and counted. Should any patient enrolled on the study miss a scheduled dose, the patient will be allowed to take the scheduled dose up to a maximum of 2 hours after that scheduled dose time. If greater than 2 hours after the scheduled dose time, the missed dose should not be taken, and the patient should take their allotted dose at the next scheduled time. Subjects should avoid grapefruit juice while on study, due to P450 interactions.

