3.3 DOSE DELAYS/MODIFICATIONS

Any toxicity observed during the course of the study could be managed by interruption of the dose of study treatment or dose reductions. Repeat dose interruptions are allowed as required, for a maximum of 4 weeks on each occasion. Study treatment can be modified per Table 2. If the reduced dose of 200 mg twice daily is not tolerable, no further dose reduction is allowed and study treatment should be discontinued.

Once dose is reduced, escalation is not permitted.

Table 2: Dose levels for olaparib dose modification

| Dose Level | Olaparib tablets |
|-------------------------|--------------------|
| 1 (Starting dose level) | 300 mg twice daily |
| -1 | 250 mg twice daily |
| -2 | 200 mg twice daily |

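### Pill diary item 6 equates half of a cycle's doses with 21 tablets, but at every Table 2 dose level 21 tablets is at most 25% of the cycle's tablets

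*Combined protocol and SAP*

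**What the plan says.** Appendix C is the form on which patients record their dosing, one form per 21-day cycle, with tablets taken twice on every day. Item 6 tells the patient: "If you miss more than half of the doses (21 tablets) in any cycle, we will have to remove you from the study". Item 7 asks the patient to "Record the date, the number of tablets you took, and when you took them", and the study-team box at the end asks for the total pills taken over days 1 to 21.

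The body of the protocol states the rule in doses and gives no tablet number. Section 3.2 says: "If a patient misses more than 50% of the doses in any given cycle, the patient will be considered inevaluable for response", and adds that the patient will be removed from the study. Sections 10.3.2 and 10.3.3 define the evaluable sets by at least half of the doses having been taken per cycle.

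Three other statements fix how tablets relate to doses:

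- Section 3.2, on strengths: "The correct number of 100mg or 150mg tablets comprising the appropriate dose should be taken at the same times each day".
- Section 3.2, on whole tablets: "The olaparib tablets should be swallowed whole and not chewed, crushed, dissolved, or divided".
- Section 3.3 and Table 2, on dose levels: 300, 250 and 200 mg twice daily, with 200 mg as the lowest level for toxicity: "If the reduced dose of 200 mg twice daily is not tolerable, no further dose reduction is allowed".

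Section 4.3.1 separately allows temporary doses of 100 mg or 150 mg twice daily during use of a CYP3A inhibitor.

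**The concern.** The sentence in item 6 gives one threshold in two units, and the units do not agree at any Table 2 dose level. The words refer to doses and match the body of the protocol. The bracketed figure refers to tablets and is far lower. The likely cause is a slip of unit, with 21 doses written as 21 tablets.

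The tablet is the unit in which adherence is handled in practice. Patients write down tablets, staff total pills on the same form, and section 3.2 states: "Compliance will be assessed by the tablet count". Item 6 gives the only removal threshold in the document that is expressed in tablets. The consequence it announces is removal from the study.

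Adherence also decides who counts as evaluable for the primary endpoint (section 10.3.2), and non-compliance is a reason for coming off therapy and off study (sections 3.5.1 and 3.5.3). Section 10.2 plans 30 evaluable patients and sets the accrual ceiling at 40 on an assumed 10% non-compliance per cycle. With numbers this small, a few removals under the wrong unit would matter.

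**Working it through.** **Inputs**

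- Cycle length: 21 days (Appendix C item 1; section 3.4).
- Doses per day: 2, every day (Appendix C item 2; section 3.2).
- Tablet strengths: 100 mg and 150 mg (sections 3.2 and 13.1.4), swallowed whole.
- Dose levels: 300, 250 and 200 mg (Table 2); 100 and 150 mg (section 4.3.1).

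**Step 1: where 21 comes from.** Doses per cycle = 21 × 2 = 42, and half is 42 / 2 = 21. The diary's figure is reproduced as a count of doses. More than half means at least 22 missed doses, and 22/42 = 52.4%.

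**Step 2: tablets per cycle.** Tablets per cycle = tablets per dose × 42. The table lists every whole-tablet combination that makes up each dose.

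| Dose | Tablets per dose | Tablets per cycle | Half | 21 tablets as a share |
|---|---|---|---|---|
| 300 mg as 2 × 150 | 2 | 84 | 42 | 25.0% |
| 300 mg as 3 × 100 | 3 | 126 | 63 | 16.7% |
| 250 mg as 150 + 100 | 2 | 84 | 42 | 25.0% |
| 200 mg as 2 × 100 | 2 | 84 | 42 | 25.0% |
| 150 mg (section 4.3.1) | 1 | 42 | 21 | 50.0% |
| 100 mg (section 4.3.1) | 1 | 42 | 21 | 50.0% |

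As a tablet count, 21 equals half only in the last two rows, and only if one tablet per dose is taken for the whole cycle.

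**Step 3: where the two readings part.** Read the bracket as more than 21 tablets, and suppose whole doses are missed.

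- Two per dose: 10 missed doses is 20 tablets and 11 is 22, so the figure is passed at 11 doses (11/42 = 26.2%). The readings disagree for 22 to 42 missed tablets, that is 11 to 21 doses.
- Three per dose: 7 missed doses is 21 tablets and 8 is 24, so the figure is passed at 8 doses (8/42 = 19.0%). The readings disagree for 22 to 63 missed tablets, that is 8 to 21 whole doses.

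If the bracket means 21 tablets or more, the lower limit becomes 21 tablets. That is still 11 whole doses at two per dose, and becomes 7 (7 × 3 = 21) at three per dose.

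**Step 4: which tablet count is likelier.** Section 13.1.4 describes 32-tablet containers and a supply for 21 + 3 = 24 days. At two per dose this is 24 × 2 × 2 = 96 tablets, exactly 3 containers. At three per dose it is 24 × 2 × 3 = 144, or 4.5 containers. The supply text thus fits two per dose. This is an inference, and the finding does not depend on it.

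**The case against.** The strongest reply is that the governing rule is consistent. Sections 3.2, 10.3.2 and 10.3.3 and the words of item 6 all speak of doses, and only a bracket on a patient form departs from them. The evaluable set is defined in section 10.3.2, not in Appendix C. Dose-level data also exist: the diary has morning and evening entries for each day, and sections 3.2 and 3.3.2.4 require missed doses to be recorded in the eCRF. The study-team box carries no 21-tablet threshold. A wrongful removal would need staff to follow the diary figure in place of section 3.2. The diary does not state tablets per dose either, so the mismatch appears only when it is read with the body text.

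Much of this stands. The analysis definitions are not themselves in error, and trained staff may well apply the rule in doses. No section says that 300 mg is given as three 100 mg tablets, so the three-tablet figures are a conditional variant.

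It does not rescue the figure. Nothing else in the document corrects it, and because the diary gives no tablets per dose, a patient holding only that form cannot detect the error. Compliance is explicitly tied to tablet counts, so the risk of the wrong unit being applied is real even if no instance is shown.

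**Conclusion.** The concern holds. At every Table 2 dose level the bracketed figure is at most 25% of a cycle's tablets, against the half that the same sentence states. At two tablets per dose, the diary's two readings give different answers for any patient who misses 11 to 21 of the 42 doses. If 300 mg were taken as three 100 mg tablets, 21 tablets would be 16.7% of the cycle and the range would widen to 8 to 21 doses.

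These ranges assume that whole doses are missed, that the dose level is constant through the cycle, and that the bracket means more than 21 tablets. The 25% maximum needs none of the assumptions about how doses are missed; it follows from the tablet strengths, the ban on dividing tablets, and the Table 2 doses.

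What is certain is a wrong number in a patient-facing statement about removal. An effect on the response-evaluable set is a possibility only. The line should be corrected.

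**What to change.** Reconcile item 6 of Appendix C with sections 3.2, 10.3.2 and 10.3.3 so that all state one threshold in one unit that works at every dispensed dose, including the one-tablet doses of section 4.3.1. A fixed number of tablets cannot do this, because tablets per dose differ between dose levels; a count or proportion of doses can. Apply the same definition when evaluability is derived from tablet counts, with the conversion from tablets to doses written down. Which threshold governs removal is for the investigator to decide, and this review proposes none.

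The cost is a one-line correction to the diary. The design, sample size and analysis do not change.

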15.4.1 Introduction

This Appendix describes the process to be followed in order to identify and appropriately report cases of Hy's Law. It is not intended to be a comprehensive guide to the management of elevated liver biochemistries.

During the course of the study the Investigator will remain vigilant for increases in liver biochemistry. The investigator is responsible for determining whether a patient meets potential Hy's Law (PHL) criteria at any point during the study.

The Investigator participates in review and assessment of cases meeting PHL criteria to agree whether Hy's Law (HL) criteria are met. HL criteria are met if there is no alternative explanation for the elevations in liver biochemistry other than Drug Induced Liver Injury (DILI) caused by the Investigational Medicinal Product (IMP).

The Investigator is responsible for recording data pertaining to PHL/HL cases and for reporting Adverse Events (AE) and Serious Adverse Events (SAE) according to the outcome of the review and assessment in line with standard safety reporting processes.

15.4.2 Definitions

15.4.2.1 Potential Hy's Law (PHL)

Aspartate Aminotransferase (AST) or Alanine Aminotransferase (ALT) \ge 3x Upper Limit of Normal (ULN) **together with** Total Bilirubin (TBL) \ge 2xULN at any point during the study following the start of study medication irrespective of an increase in Alkaline Phosphatase (ALP).

15.4.2.2 Hy's Law (HL)

AST or $ALT \ge 3x$ ULN together with $TBL \ge 2xULN$, where no other reason, other than the IMP, can be found to explain the combination of increases, e.g., elevated ALP indicating cholestasis, viral hepatitis, another drug.

For PHL and HL the elevation in transaminases must precede or be coincident with (i.e. on the same day) the elevation in TBL, but there is no specified timeframe within which the elevations in transaminases and TBL must occur.

15.4.3 Identification of Potential Hy's Law Cases

In order to identify cases of PHL it is important to perform a comprehensive review of laboratory data for any patient who meets any of the following identification criteria in isolation or in combination:

- $ALT \ge 3xULN$
- $AST \ge 3xULN$
- TBL $\geq 2xULN$

The Investigator will without delay review each new laboratory report and if the identification criteria are met will:

- Determine whether the patient meets PHL criteria (see Definitions within this Appendix for definition) by reviewing laboratory reports from all previous visits
- Promptly enter the laboratory data into the laboratory CRF

15.4.4 Follow-up

15.4.4.1 Potential Hy's Law Criteria not met

If the patient does not meet PHL criteria the Investigator will:

• Perform follow-up on subsequent laboratory results according to the guidance provided in the Clinical Study Protocol.

15.4.4.2 Potential Hy's Law Criteria met

If the patient does meet PHL criteria the Investigator will:

- Monitor the patient until liver biochemistry parameters and appropriate clinical symptoms and signs return to normal or baseline levels, or as long as medically indicated
- Investigate the etiology of the event and perform diagnostic investigations.
- Complete the three Liver CRF Modules as information becomes available
- If at any time the PHL case meets serious criteria, report it as an SAE using standard reporting procedures

15.4.4.3 Review and Assessment of Potential Hy's Law Cases

The instructions in this Section should be followed for all cases where PHL criteria are met.

No later than 3 weeks after the biochemistry abnormality was initially detected, the Investigator will follow the instructions below.

If there is an alternative explanation for the ALT or AST and TBL elevations, a determination of whether the alternative explanation is an AE will be made and subsequently whether the AE meets the criteria for a SAE:

- If the alternative explanation is **not** an AE, record the alternative explanation on the appropriate CRF
- If the alternative explanation is an AE/SAE, record the AE /SAE in the CRF accordingly and follow the AZ standard processes

If there is **no** explanation that would explain the ALT or AST and TBL elevations other than the IMP:

- Report an SAE (report term 'Hy's Law') according to AstraZeneca standard processes.
 - The 'Medically Important' serious criterion should be used if no other serious criteria apply

- As there is no alternative explanation for the HL case, a causality assessment of 'related' should be assigned.

If, there is an unavoidable delay, of over 3 weeks, in obtaining the information necessary to assess whether or not the case meets the criteria for HL, then it is assumed that there is no alternative explanation until such time as an informed decision can be made:

- Report an SAE (report term 'Potential Hy's Law') applying serious criteria and causality assessment as per above
- Continue follow-up and review according to agreed plan. Once the necessary supplementary information is obtained, repeat the review and assessment to determine whether HL criteria are met. Update the SAE report according to the outcome of the review

